3.0 Intervention to be studied (if applicable)

Side-by-side integration of AT and PT has not been examined and we propose to conduct a clinical trial in which for two weeks daily (Monday-Friday), 20 children between the ages of 3-18 years will be randomly assigned into one of two groups: 1) collaborative intervention: 45 minutes of AT immediately followed by 30 minutes of PT or 2) PT only intervention: 30 minutes. During the collaborative intervention of week 1, oil pastels will be the media and week 2 gouache painting without brush.

Treatment: 45 minutes of AT closely followed by 30 minutes of PT OR 30 minutes of PT.

AT treatments will seek to reduce sympathetic dominance/physiological and emotional distress. Oil pastels will be used for Days 1-5 and gouache painting for days 6-10. Art therapy is a collaborative, interactive, and iterative process that evolves across the session between the child and art therapist, as such, outside of the actual change in medium, there is no study specific art therapy prescription or protocol. Art therapy sessions will occur in the child's room.

PT treatments will seek to prevent physical deconditioning and encourage mobility, ambulation, and selfcare participation based on participant's ability. Physical therapy sessions will occur in the child's room and on the HCT unit.

The same art and physical therapist and art therapist will conduct children's session across the 2-week study duration. This art and physical therapist commonly work on the HCT unit. The coordinator again will monitor all sessions to ensure the following of study procedures.

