10.0 Study Design / Methods

Design: Randomized clinical trial to compare collaborative AT and PT to only PT in children undergoing HCT.

Using excel, the study coordinator will randomize each participant to either the PT and AT or PT only group. Each group will be assigned 10 participants.

Power

With a recruitment expectation of 30 participants, we expect a 30% drop out rate leaving 20 enrolled participants and feel confident that this study's aim 2 and 3 will be successfully powered to identify statistical significance ($p<0.05$) in outcomes. For Aims 2 and 3 which involve the collection of clustered data for HRV, SAM, and walking distance, in order to identify a medium effect, 80% or 90% power will be achieved with 61 or 82 measurement points respectively.^{54,55,66,67} Accounting for a dropout rate of 30%, the expected number of participants is 20. With 10 participants in the intervention group, 100 measurement points for HRV, SAM, and walking distance each are expected; thus, ensuring adequate power for aim 2 and 3.

For the PEDI CAT and 6MWT, to achieve 80% power, the projected sample size in each group is estimated to be 16 and 20; therefore, we proposed that we may not be adequately powered for aim 1.^{51,68} However, findings attributed to aim 1 will provide pilot data to inform a larger randomized control trial. Although aim 1 may not be adequately powered, the published minimal detectable change (MDC) for the PEDI CAT selfcare and mobility domains are 2.2 and 2.5 respectively while the Minimally Clinically Important Difference (MCID) for the 6MWT is 7%.^{69,70} Although, power to find a statistically significant difference may be inadequate, we expect to observe this level/magnitude of improvement in our proposed study. Variation values from this aim will provide data that are essential to guide future research.

Data Analyses

Aim 1: In children undergoing HCT during in-patient care, do a randomized group receiving a combination of Physical Therapy (PT) plus Art Therapy (AT) have improved functional activity level outcomes of self care and mobility as measured by the Pediatric Evaluation of Disability Inventory Computerized Adaptive Test and the 6-Minute Walk Test, compared with a group receiving PT only.

Hypothesis 1: Children receiving the combined intervention of PT plus AT will demonstrate greater improvements in self care and mobility skills.

Statistical Test: Independent sample t-tests

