Aim 2: Do children receiving PT plus AT have physiological (sympathetic or parasympathetic) and emotional responses to oil pastels and gouache as measured by respiratory sinus arrhythmia derived from heart rate variability and Self-Assessment Manikin scores during each of the daily AT sessions.

Hypothesis 2: Oil pastels or gouache AT will generate a RSA value in the direction of needed parasympathetic activity and balance the emotions of valence, arousal, and dominance.

Statistical Test: Repeated measures generalized linear regression

Aim 3: In children receiving PT plus AT, determine if there is a stronger association between the RSA values of oil pastels or gouache AT and an increased walking distance as measured by accelerometry during daily PT sessions.

Hypothesis 3: The media that best generates a parasympathetic RSA value and emotional balance will be associated with a greater walking distance.

Statistical Test: Repeated measures generalized linear regression

Data Collection

The 10-day intervention will begin on approximately Day 15 of HCT. Pre-test (Pediatric Evaluation of Disability Inventory and 6-Minute Walk Test) will be collected on Day 14. The same post-test data will be collected the day following the tenth day of intervention.

During the 10 days of intervention, the Self Assessment Manikin, heart rate variability, and walking distance will be collected daily.

The study coordinator will be responsible for storing all data. All documentation and data concerning each participant will be coded to protect confidentiality. All data collection and storage processes and locations will use study equipment (i.e., heart rate variability monitors, computers, College of Health Professions DA server) that is password protected, encrypted, and behind the MUSC firewall. All study related equipment will be locked in the office of the PI when not in use. There will be no transfer of data to a third party.

Procedures

- 1) IRB approval
- 2) Begin participant enrollment
- 3) Collaborate with HCT team to initiate recruitment and share study flyer
- 4) PI will obtain informed consent from participants in the hospital or electronically through MUSC secure email.
- 5) Randomize participant to AT and PT or PT only
- 6) Approximately Day 14 of HCT complete pre-test (Pediatric Evaluation of Disabilities Inventory and 6-Minute Walk Test)

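### The Procedures list randomises before the Day 14 pre-test, and nothing keeps the arm from the tester or family until the Aim 1 baseline is recorded.

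*Combined protocol and SAP*

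**What the plan says.** The numbered Procedures in section 10.0 put consent at step 4. Step 5 is "Randomize participant to AT and PT or PT only", with no study day. Step 6 is "Approximately Day 14 of HCT complete pre-test (Pediatric Evaluation of Disabilities Inventory and 6-Minute Walk Test". Treatment (Days 15 to 24) and the post-test (about Day 25) follow as steps 7 and 8.

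Section 9.0 places consent on or before about Day 13, pre-testing on Day 14 and the first session on Day 15. It does not place randomisation.

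On who does what, section 10.0 states: "Using excel, the study coordinator will randomize each participant to either the PT and AT or PT only group". Section 4.0 gives collection and scoring of both the pre-test and the post-test to the study coordinator/PhD student. Section 3.0 has the coordinator monitor all sessions.

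The allocation is fixed in size: "Each group will be assigned 10 participants". For Aim 1 the only analysis named is independent-sample t-tests. Hypothesis 1 is worded in terms of greater improvement in the combined arm.

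No section mentions blinding, masking, allocation concealment, a separate assessor, or holding the arm back until the baseline is complete.

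**The concern.** Aim 1 is the trial's only randomised comparison, so it is where the baseline has to be free of the allocation. On the listed order, the person giving the PEDI-CAT and 6MWT at Day 14 may already know the arm, and so may the child and parents. The walk test depends on effort and encouragement, so such knowledge could plausibly alter it, in either direction. That is general reasoning and not an effect shown in the documents.

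If the outcome is change from pre-test, a distorted baseline appears as a treatment difference, or hides one. Section 10.0 intends the Aim 1 findings to inform a larger randomised trial, so a biased estimate could carry forward. Aims 2 and 3 are not touched, because they are analysed within the combined arm and do not use the pre-test.

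**Working it through.** The plan gives no figure for this point, so there is none to reproduce. The check has four parts.

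**1. Order.** Steps 4 to 8 (consent, randomise, pre-test about Day 14, treatment Days 15 to 24, post-test about Day 25) follow the calendar in section 9.0 wherever a day is given. Consent by about Day 13 leaves room to randomise before Day 14. No section states a different order.

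**2. How a baseline distortion enters Aim 1.** Suppose the pre-test in one arm is shifted by b.
- Change scores: the contrast is (post − pre) in one arm minus (post − pre) in the other. It moves by b in absolute size, so the share passed on is 1.0.
- Post-test scores only: the pre-test does not appear. The share passed on is 0.

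The plan does not say which applies. The wording of Hypothesis 1 points to change.

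**3. Illustrative size under change scores.** Inputs: 10 per arm (section 10.0); two-sided 5% level (section 10.0 gives p<0.05; two-sided is assumed); no true effect; b of 0.1, 0.2 or 0.3 SD of the change score. The values of b are assumed and come from no document.

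Noncentrality = b / √(1/10 + 1/10) = b / 0.447. Degrees of freedom = 18, critical value = 2.101.

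| Assumed b (SD) | Noncentrality | Rejection rate |
|---|---|---|
| 0 | 0 | 5.0% |
| 0.1 | 0.224 | 5.5% |
| 0.2 | 0.447 | 7.1% |
| 0.3 | 0.671 | 9.7% |

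With a t-test on post-test scores alone, the rate stays at 5.0% for every b in the pre-test.

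**4. What a fixed 10:10 split still reveals.** For a random sequence of 10 and 10:
- Allocations that are certain because one arm is already full: 10/11 + 10/11 = 20/11 = 1.8 of 20 on average.
- Correct guesses by someone who keeps a tally and names the emptier arm: 10 + ½ × (4¹⁰ / C(20,10) − 1) = 10 + ½ × (1,048,576 / 184,756 − 1) = 12.3 of 20, against 10 by chance.

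Reordering therefore protects the baseline well, but not perfectly.

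**The case against.** Several points on the other side have force.

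- **The list may not be a strict sequence.** "Begin participant enrollment" is step 2 and "Collaborate with HCT team to initiate recruitment and share study flyer" is step 3, which cannot be literal order, and randomisation carries no day. This stands as a caution. Even so, steps 4 to 8 do run in order, and they are what staff would follow.
- **Knowledge of the arm is not stated.** A reader might infer that the plan has the family told, or the tester informed, before Day 14. It does not say so. It only fails to prevent it, and the study coordinator and the study coordinator/PhD student could be two people. This stands, and it is why the point is about a missing safeguard and not a demonstrated bias.
- **Early losses.** A reader might also infer that children will be randomised and then lost before any baseline exists. The documents do not support this. Section 3.0 has "20 children between the ages of 3-18 years will be randomly assigned into one of two groups", and section 10.0 says "we expect a 30% drop out rate leaving 20 enrolled participants". Both can be read as placing the planned losses before assignment, so no such claim is made here.
- **Low stakes.** Aim 1 is declared possibly underpowered and pilot. One stated use is its variation values, and a uniform shift in one arm's baseline leaves within-arm variance unchanged. This stands. Only the effect estimate is exposed.
- **The larger problem is the post-test.** The coordinator sees every session, so post-test scoring is unblinded under either analysis. This stands, and reordering does not cure it.
- **A bare swap creates a new risk.** If the person who has just scored the baseline then draws the arm in Excel, the allocation could be steered by the score. If that person holds a ready-made list, the swap hides nothing. This is correct, and separate custody of the list is therefore part of the fix.

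**Conclusion.** The point holds as a modest, inexpensive improvement to the design. As written, the plan allows the Aim 1 baseline to be measured with the arm known, when the existing Day 14 to Day 15 gap permits a better order.

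The conclusion rests on three conditions: the listed order is followed, the coordinator role that randomises also tests, and Aim 1 is analysed as change. If post-test scores alone are compared, the consequence for the t-test is nil.

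It would be tempting to read the 5.5% to 9.7% range as the trial's actual error rate. It is not: it follows from assumed shifts of 0.1 to 0.3 SD, and the documents support no particular value or direction.

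**What to change.** Make one combined change in section 10.0:

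1. Swap steps 5 and 6. The Day 14 pre-test is completed and recorded before the arm is disclosed to anyone who tests or to the family, and disclosure takes place before the Day 15 session. State this timing in the text.
2. Have the allocation sequence generated in advance and held by an existing team member who neither tests nor obtains consent, for example a co-investigator. That person releases each arm only after the baseline is locked. Without this, the swap achieves little.
3. State in the protocol and the report that the post-test assessor is not blinded.

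The cost is two reordered steps and a few sentences, with no added visits, tests or staff. The downsides are about one day's notice of allocation for the art therapist, a small coordination task for the list holder, and the partial predictability of a fixed 10:10 split.

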9.0 Consent Process

Informed consent will be sought upon each child's admission to MUSC Shawn Jenkins Children's Hospital. It will occur approximately on or before Day 13 of the HCT. Day 14 will be for pre-testing and day 15 for start of intervention. Children's authorized representative will have at least 24 hours prior to study intervention initiation.

Consent may be obtained in person at the hospital or using an electronic consent.

For in person consents, the PI will obtain informed consent from parents or legal guardians at the MUSC Shawn Jenkins Children's Hospital.

The PI will communicate by phone or email with the parent or legal guardian to establish a time to seek informed consent at the hospital OR discuss the use of an electronic consent. If an electronic consent is used, the PI will email the consent to the parent or legal guardian using secure MUSC email. Then the PI will contact the parent or legal guardian by phone to review the informed consent and answer any questions. If the parent or legal guardian wishes to enroll in the study, they will sign the informed consent and return to the PI through the MUSC email system.

Assent will be obtained from each individual child or adolescent at the same time that the informed consent is obtained from parents. If informed consent is carried out electronically, the parent will be asked to document the child or adolescent's assent using MUSC email communication.

If a child withdraws assent prior to a study session, parents will be notified. If the child withdraws assent for a session for 3 days in a row, the child will be withdrawn from the study. If assent is less than 3 days, then missed days will be added to the study duration until 10 days are completed.

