- 7) Day 15-24 of HCT: 45 minutes of AT and 30 minutes of PT OR 30 minutes of PT only. Heart rate variability, Self Assessment Manikin, accelerometry collected across sessions.
- 8) Approximately Day 25 of HCT complete post-test (Pediatric Evaluation of Disabilities Inventory and 6-Minute Walk Test)
- 9) Data analyses and dissemination.

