12.0 Data Management

All documentation and data concerning each participant will be coded to protect confidentiality. All data collection and storage processes and locations will use study equipment (i.e., heart rate variability monitors, computers, College of Health Professions DA server) that is password protected, encrypted, and behind the MUSC firewall. All study related equipment will be locked in the office of the PI when not in use. There will be no transfer of data to a third party.

13.0 Provisions to Monitor the Data to Ensure the Safety of Subjects (if applicable)

All documentation and data concerning each participant will be coded to protect confidentiality. All data collection and storage processes and locations will use study equipment (i.e., heart rate variability monitors, computers, College of Health professions DA server) that is password protected, encrypted, and behind the MUSC firewall. All study related equipment will be locked in the office of the PI when not in use. There will be no transfer of data to a third party.

Children undergoing HCT will experience symptoms related to the HCT and may experience additional medical complications. Our study involving art and physical therapy interventions will only be carried out during the in-patient phase, which will be helpful when considering adverse effects because a variety of

healthcare professionals will be at hand to possibly prevent and ameliorate any adverse events. For example, prior to each daily session, the art and/or physical therapist will ask the child's nurse if the patient is medical stable to participate. If the nurse, reports that the child is not medically stable, then the child's session will be postponed until stable.

Common symptoms following transplant include fatigue and deconditioning which is associated with lower strength and endurance. We believe children' participation in this study will lead to temporary reports of elevations in fatigue, weakness, and poorer endurance symptoms; however, we will not view these as adverse events since these symptoms are also common to increases in activity level that will be generated by art and physical therapy.

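### Ten weekday sessions from HCT Day 15 end on Day 26 to 28, not Day 24, and with pastels always first, a stop after sessions 5 to 9 removes only gouache, so 100 points is a maximum

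*Combined protocol and SAP*

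**What the plan says.** Section 3.0 sets the schedule as "for two weeks daily (Monday-Friday" and fixes the order of the media in the art therapy (AT) arm: "Oil pastels will be used for Days 1-5 and gouache painting for days 6-10".

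Section 10.0 dates the course in two ways. Data Collection starts a 10-day intervention on about Day 15 and gives a relative rule for the post-test: "The same post-test data will be collected the day following the tenth day of intervention". The Procedures list gives fixed days: "Day 15-24 of HCT: 45 minutes of AT and 30 minutes of PT OR 30 minutes of PT only", then "Approximately Day 25 of HCT complete post-test".

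Three rules govern interrupted courses:
- Section 9.0, refused sessions: "missed days will be added to the study duration until 10 days are completed". There is one limit: "If the child withdraws assent for a session for 3 days in a row, the child will be withdrawn from the study".
- Section 13.0, unstable days: the "session will be postponed until stable". Treatment is also deferred during an ICU stay and continues after a move to an ordinary ward room.
- Section 13.0, discharge home: the intervention ends, whether or not ten days have been given.

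The Power paragraph of section 10.0 expects 100 measurement points per outcome from 10 AT children, against requirements of 61 points (80% power) and 82 points (90% power). The 30% dropout allowance is applied to whole participants.

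**The concern.** The listed days and the weekday schedule cannot both be followed. The post-test supplies the Aim 1 outcomes (PEDI CAT and 6-Minute Walk Test) in both arms, so its timing relative to session 10 should be unambiguous.

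The second issue concerns Aims 2 and 3, which compare the two media within the AT arm. With a fixed order and a stop at discharge, early stopping does not thin the two media equally. It removes the later one, and each postponed day moves gouache closer to discharge. The children who supply gouache data are then those who stay in hospital longer, while pastel data come from nearly everyone. A count of 100 points with no allowance for sessions lost within a child hides this.

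**Working it through.** **1. The plan's own figures.** Day 15 to Day 24 is 24 − 15 + 1 = 10 calendar days, and Day 25 is the next day. These dates reproduce only if sessions run on ten consecutive days, weekends included. The 100 points are 10 children × 10 sessions, or 50 pastel and 50 gouache, which requires every AT child to complete all ten sessions.

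**2. The calendar with weekday sessions.** Inputs: sessions on Monday to Friday only (section 3.0), first possible day Day 15, and post-test the day after session 10 (section 10.0, Data Collection).

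| Day 15 falls on | First session | Tenth session | Post-test | Sessions possible by Day 24 |
|---|---|---|---|---|
| Mon | Day 15 | Day 26 | Day 27 (Sat) | 8 |
| Tue | Day 15 | Day 28 | Day 29 | 8 |
| Wed | Day 15 | Day 28 | Day 29 | 8 |
| Thu | Day 15 | Day 28 | Day 29 | 7 |
| Fri | Day 15 | Day 28 | Day 29 | 6 |
| Sat | Day 17 | Day 28 | Day 29 (Sat) | 6 |
| Sun | Day 16 | Day 27 | Day 28 (Sat) | 7 |

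From first to tenth session the course spans 12 days when it begins on a Monday and 14 otherwise, so no start weekday fits a ten-day window. The error is 26 − 24 = 2 to 28 − 24 = 4 days for the last session, and 27 − 25 = 2 to 29 − 25 = 4 days for the post-test.

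**3. Which medium is lost.** I read the numbered days in section 3.0 as sessions, because section 9.0 counts completed days. A child who stops after session s, with s from 5 to 9, loses 10 − s sessions, all gouache. If d of the 10 AT children do so:

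gouache = 50 − d(10 − s), pastel = 50, total = 100 − d(10 − s).

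The documents give no discharge days, so the values of d and s below are assumptions that show a range.

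| Children stopping (d) | After session 7: gouache / total | After session 5: gouache / total |
|---|---|---|
| 1 | 47 / 97 | 45 / 95 |
| 3 | 41 / 91 | 35 / 85 |
| 5 | 35 / 85 | 25 / 75 |

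A stop before session 5 loses all five gouache sessions and some pastel sessions as well.

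**4. Against the stated targets.** Taking 61 and 82 as given, 100 − 82 = 18 points can be lost before the total falls below the higher target, and 100 − 61 = 39 before it falls below the lower. No cell in step 3 is below 61, and only the most extreme is below 82. The targets are totals, however. If all losses were gouache, 82 would be met at 50 pastel and 32 gouache, and 61 at 50 and 11. Meeting a total therefore says little about gouache.

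**5. What randomised order would gain in precision.** Treating points as independent, the standard error of the difference between media, relative to 50/50, is √(1/n₁ + 1/n₂) ÷ √(2/50):
- 50/41 gives 1.053; 45.5/45.5 gives 1.048.
- 50/35 gives 1.102; 42.5/42.5 gives 1.085.
- 50/25 gives 1.225; 37.5/37.5 gives 1.155.

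Equal counts gain about 0.5%, 1.6% and 6%. For a within-child contrast the gain is nil: a child with five sessions of one medium and two of the other contributes variance proportional to 1/5 + 1/2 in either order.

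**The case against.** The strongest reply on dates is that a governing rule already exists. Data Collection ties the post-test to the tenth intervention day, section 9.0 extends the course until ten days are done, and both the start and Day 25 are approximate. Section 3.0 also speaks of week 1 and week 2, which suggests Monday starts and an error of only 2 days. Most of this stands. It means that the listed days are wrong labels, not that they control the trial. But the ten-day window itself carries no such qualifier, and the discrepancy always runs in the same direction. Even a Monday start on Day 13, which would finish on Day 24, would span 12 days.

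On the media, the reply is that no discharge figures are given, that moving to an ordinary room does not stop treatment, that withdrawal after repeated refusals is a participant loss of the kind the 30% allowance covers, and that a repeated measures model accepts unequal counts. This also stands, and step 5 shows that balancing the counts buys almost no precision. It does not change the direction of the loss, or the fact that 100 requires complete courses.

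Three stronger readings are tempting and not supported:
- That Day 24 cuts the course short and removes points. Sections 9.0 and 13.0 add or postpone missed sessions, so Day 24 is not a stopping rule.
- That Aims 2 and 3 miss their point targets. Nothing in the documents shows losses of that size.
- That Aim 1 will be measured after 6 to 8 sessions. That would require staff to put an approximate Day 25 ahead of the explicit rule.

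**Conclusion.** The concern holds in a limited form. The listed window and post-test day are 2 to 4 days too early for ten weekday sessions from Day 15 (2 days for a Monday start) and conflict with section 10.0's own post-test rule. This rests only on the weekday schedule and a Day 15 start.

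The fixed order combined with the stop at discharge means that any stop after sessions 5 to 9 removes gouache only. Gouache data are then selected by length of stay, and 100 points (50 per medium) is a maximum rather than an expectation. This rests on reading the numbered days as sessions. The size of the loss cannot be computed from the documents, and no shortfall against 61 or 82 is established. The confounding of medium with week is a separate matter and is not claimed here.

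**What to change.** - In sections 3.0 and 10.0, define the intervention as ten completed weekday sessions, about HCT Day 15 to Day 26–28, and delete the Day 15–24 window and the Day 25 post-test. State that the medium changes after five completed sessions.
- Set the post-test for the day after session 10 (about Day 27–29) or the next working day, or at discharge if that comes first. Courses that finish on a Friday give a Saturday test in 3 of the 7 cases above; moving it to Monday gives Day 29 to 31. The protocol does not currently say when a child discharged early is tested.
- In the Power paragraph, restate 100 points as a maximum of 50 per medium.
- Randomise the order of the two five-session medium blocks for each AT child, so that early stopping does not fall systematically on one medium.

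The cost is text edits, one extra assignment per AT child, and both media on hand from the start. The gain is balance between media and less selection by length of stay. Lost sessions are not recovered and precision barely changes.
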